5.3.2. Efficacy Period

The efficacy period in study 9HB01EXT will be used for the evaluation of bleeding and rFIXFc consumption endpoints. For a subject to have an evaluable efficacy period over the duration of study 9HB01EXT, he must have >0 day of treatment for an episodic regimen and at least 2 prophylactic injections for prophylactic regimens.

The start and end, and the total duration of the efficacy period for a given treatment regimen in 9HB01EXT is the same as the start and end, and the total duration of that treatment regimen defined in Section 5.3.1 with the following exception to the definition of start, and the adjustments necessary due to surgical/rehabilitation periods.

Exception to the Definition of Start

For subjects who entered study 9HB01EXT during a surgical/rehabilitation period, if they are to be on a prophylactic regimen in study 9HB01EXT, then the efficacy period for the prophylactic regimen will start at the time of the first prophylactic dose following the end of the surgical/rehabilitation period (see Section 5.3.3). If they are to be on the episodic regimen in study 9HB01EXT, then the efficacy period for the episodic treatment regimen will start at 00:01 on the day following the end of the surgical/rehabilitation period (see Section 5.3.3).

Adjustments Due to Surgical/Rehabilitation Periods

For analysis purposes, the efficacy period for a given treatment regimen will be adjusted for all surgical/rehabilitation periods (major and minor). The start and end of the efficacy period for a given treatment regimen is adjusted as follows:

- For subjects on a prophylactic regimen before the start of a surgical/rehabilitation period, the efficacy period for the prophylactic regimen continues up to the last dose (for prophylaxis or a bleed) before the start of the surgical/rehabilitation period.
- For subjects on the episodic regimen before the start of a surgical/rehabilitation period, the efficacy period for the episodic regimen continues up to 1 minute before the start of a surgical/rehabilitation period.
- For subjects on a prophylactic regimen following the end of a surgical/rehabilitation period, the efficacy period for the prophylactic regimen starts or restarts (depending on whether there is a treatment regimen change during the surgical/rehabilitation period) at the first prophylactic dose following the end of the surgical/rehabilitation period.
- For subjects on the episodic regimen following the end of a surgical/rehabilitation period, the efficacy period for the episodic regimen starts or restarts (depending on

whether there is a treatment regimen change during the surgical/rehabilitation period) at 00:01 on the day following the end of the surgical/rehabilitation period.

Start and end dates/times for the efficacy period for given treatment regimens and treatment regimen changes will be adjusted for each surgery (major or minor) as necessary.

For subjects on a prophylactic regimen before the start of a surgical/rehabilitation period, the interval of time between the last dose before a surgical/rehabilitation period and the start of the surgical/rehabilitation period will not be attributed to the efficacy period for the prophylactic regimen. By definition, there should not be any treated bleeding episodes in this interval of time.

For subjects on a prophylactic regimen following the end of a surgical/rehabilitation period, bleeding episodes that occur after discharge from a rehabilitation facility but before the next prophylactic dose will be attributed to the surgical/rehabilitation period and hence not counted towards the annualized bleeding rate.

Adjustments Due to Large Injection Intervals

For analysis purposes, the efficacy period will also be adjusted to account for large intervals between injections resulting from missing data. Time between any 2 adjacent rFIXFc injections of greater than 42 days within a prophylactic treatment regimen will be removed from the efficacy period. The efficacy period prior to each such interval will end at the time of the first injection of this interval and restart (or start if it is the first interval of a treatment regimen) at the time of the second injection of this interval. The efficacy period will be adjusted for each identified interval that is not within a surgical/rehabilitation period. Treatment regimens considered for large interval adjustment include individualized prophylaxis, weekly prophylaxis, and personalized prophylaxis regimen with at least 2 routine prophylactic injections (additional injections are not considered due to the sporadic nature of these injections). No adjustment for large injection intervals will be made for episodic treatment regimens.

5.3.3. Surgical/Rehabilitation Period

The broadest span of time for the surgical/rehabilitation period in study 9HB01EXT is from the first dose of rFIXFc in study 9HB01EXT given for the surgery (i.e., the pre-surgery dose) up to 1) 1 minute before the first regular prophylactic dose after the last day of post-operative care/rehabilitation for subjects on prophylactic regimens and/or 2) 23:59 on the last day of the surgical/rehabilitation period for subjects on the episodic regimen. If dose(s) labelled for a surgical reasons which do not correspond to a surgery will be re-classified as 'OTHER' and will not be used in the determination of the surgical/rehabilitation period. Since not all subjects will have these events, specific considerations for the start and end of the surgical/rehabilitation period are as follows:

Start of the surgical/rehabilitation period:

- Date/time of the first pre-surgical dose. In general, if an injection for a pre-surgical dose is recorded in the eCRF, the reason for the injection should be labelled as "prophylaxis pre-operative". If an injection for pre-surgical dose is recorded in the EPD, the reason will be labelled as "surgical prophylaxis". If the date/time of surgery is complete, a pre-surgery dose is any dose labelled for a surgical reason on the day of, or the day before surgery, which is prior to the start date/time of the surgery. If the time of surgery is missing or 00:00 (as sometime occurs for minor surgeries), only

injections labelled as “prophylaxis pre-operative” on the day of surgery should be taken as a pre-surgical dose along with any other doses labelled for a surgical reason on the day before surgery. If there is more than one pre-surgical dose, then the first one should be selected (a pre-surgical dose can be administered the day before the surgery).

- If there is no pre-surgical dose but there was a prophylaxis dose or dose given for ‘OTHER’ reason prior to the surgery on the day of or the day before surgery, the last of these doses should be selected.
- If there is no pre-surgical dose, a prophylaxis dose, or dose for ‘OTHER’ reason prior to the surgery on the day of or the day before surgery then select the start date/time of the surgery. If the time was not recorded or recorded as 00:00 then select the date and impute 00:01 for the time.

End of the surgical/rehabilitation period:

If the treatment regimen after the surgical/rehabilitation period is a prophylactic regimen, then the end of the surgical/rehabilitation period is:

- 1 minute before the first prophylactic dose on or after the last date among the dates for discharge from the hospital, post-operative visit 1, post-operative visit 2, the end of rehabilitation.
- If all of the dates mentioned above are missing, then select the first prophylactic dose after the date/time for the end of surgery. If the surgery time was not recorded or recorded as 00:00, then select the surgery date and impute 23:59 for the time. If the end date of the surgery is missing, then select the start date of the surgery and impute 23:59 for the time.
- If there are no prophylaxis doses following the latter of the 6 dates mentioned above, then select the latter of the dates and impute 23:59 for the time if otherwise there is no time associated with the given date (e.g., the subject completed the surgical/rehabilitation period but received no further prophylactic doses).
- If the overall end of study is declared while the subject is still in the surgical/rehabilitation period, then select the date of the end of study and impute 23:59 for the time.

If the treatment regimen after the surgical/rehabilitation period is the episodic regimen, then the end of the surgical/rehabilitation period is:

- Imputed as 23:59 on the last date among the dates for discharge from the hospital, post-operative visit 1, post-operative visit 2, and the end of rehabilitation
- If all of the dates mentioned above are missing, then select the date of the end of surgery and impute 23:59 for the time. If the end date of the surgery is missing, then select the start date of the surgery and impute 23:59 for the time.

Two exceptions are noted:

- If 2 (or more) major surgeries are performed without an intervening discharge from the hospital, then the first surgical/rehabilitation period will end 1 minute before the

start of the next surgery and the second surgical/rehabilitation period will end as described above.

- If minor surgery is performed during post-operative care or rehabilitation, then the surgical/rehabilitation period for the minor surgery will start and end on the day of the minor surgery, at 00:01 and 23:59, respectively, if times are not otherwise provided or recorded as 00:00. The surgical/rehabilitation period for the major surgery will include the minor surgery (i.e., the surgical/rehabilitation period for the major surgery does not stop and restart around the minor surgery) and will end as otherwise defined.

Within the total surgical/rehabilitation period, the time is divided into:

- Intraoperative period: from the date/time of the pre-surgery rFIXFc dose to the date/time of the end of surgery
- Post-operative care period: from the date and time plus 1 minute following the end of surgery to the last dose of rFIXFc given for the surgery, including doses given to prevent bleeding during the post-operative period
- Post-operative rehabilitation period: from the date following the last day of post-operative care to the end of the surgical period as described above

The surgical/rehabilitation period will be determined in the same manner for both major and minor surgeries.

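### SAP 5.3.3: for minor surgery with same-day discharge covered by a routine prophylaxis dose, the end rule selects the dose that starts the period, so the post-surgery interval stays in the efficacy period

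*SAP*

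**What the plan says.** SAP 5.3.3 builds the surgical/rehabilitation period from dose records, by the same method for major and minor surgery.

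- **Start, no dose labelled surgical.** The rule covers this case directly: "If there is no pre-surgical dose but there was a prophylaxis dose or dose given for ‘OTHER’ reason prior to the surgery", then the latest such dose from the surgery date or the date before it is taken. A routine dose on the morning of surgery therefore opens the period.
- **End, prophylactic regimen, main bullet.** The period ends "1 minute before the first prophylactic dose on or after the last date among the dates for discharge from the hospital", post-operative visits 1 and 2, and the end of rehabilitation.
- **End, none of the four dates recorded.** "If all of the dates mentioned above are missing, then select the first prophylactic dose after the date/time for the end of surgery".
- **Opening sentence of the section.** For prophylactic regimens the broadest span runs to "1 minute before the first regular prophylactic dose after the last day of post-operative care/rehabilitation for subjects on prophylactic regimens".

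SAP 5.3.2 then adjusts the efficacy period. For a subject on prophylaxis it stops at the last dose before the surgical period starts and resumes at the first prophylactic dose after that period ends. It adds that "the interval of time between the last dose before a surgical/rehabilitation period and the start of the surgical/rehabilitation period will not be attributed"; those days do not count as efficacy time. SAP 6.5.4 and 7.1 keep both major and minor surgical periods out of the consumption and bleeding analyses.

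**The concern.** The main end bullet compares a dose with a calendar date and accepts a dose on that date. It does not ask whether the dose came before or after the operation. If the latest recorded date is the day of surgery, a routine dose given that morning qualifies as the end dose, although the start rule has already made it the start. The period then closes before it opens.

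At stake is which days, bleeds and doses feed ABR and annualized consumption, both secondary endpoints. The SAP means to keep peri-operative bleeding and dosing out of them. In SAP 5.3.2 it even assigns to the surgical period any bleed between discharge from a rehabilitation facility and the next prophylactic dose. Under the literal end bullet the post-operative interval is not kept out. A programmer who meets a negative duration also has no rule for resolving it, because the section's other sentences give a different answer.

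**Working it through.** The plan states no figure for this, so the check applies the rules to an assumed case.

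**Assumed case.** Surgery 10:00 to 11:00; discharge at 15:00 the same day; no post-operative visit or rehabilitation date. A routine prophylaxis dose D0 is given at 08:00 that day. The previous dose is D-1 and the next is D1, each k days away. SAP 3.2.1.2 has weekly dosing (k = 7) and individualized dosing every 8 to 16 days; I use k = 7, 8, 14 and 16. Protocol 5.3.3 has no Visits 3 and 4 for minor surgery, so discharge can be the only recorded date.

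**Step 1, start.** No dose is labelled surgical, so the start is D0, 08:00.

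**Step 2, end, main bullet read by date.** The last of the four dates is the surgery date. The first prophylactic dose on or after that date is D0. The end is 07:59 and the length is 07:59 - 08:00 = -1 minute, whatever k is.

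**Step 3, end, dose required to follow the surgery, or the last day as in the opening sentence.** The dose is D1. The end is D1 minus 1 minute and the length is 1440k - 1 minutes, which for k = 7 is 10,079.

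**Step 4, efficacy period.** Under both readings it stops at D-1. Under the literal bullet it resumes at D0, so D0 - (D-1) = k days are removed. Under the intended reading it resumes at D1, so D1 - (D-1) = 2k days are removed.

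| k (days) | Period length, literal (min) | Period length, intended (min) | Days removed, literal | Days removed, intended |
|---|---|---|---|---|
| 7 | -1 | 10,079 | 7 | 14 |
| 8 | -1 | 11,519 | 8 | 16 |
| 14 | -1 | 20,159 | 14 | 28 |
| 16 | -1 | 23,039 | 16 | 32 |

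**Step 5, effect on one subject's ABR.** SAP 7.1.1 gives ABR = bleeds / efficacy days × 365.25. Assume weekly dosing, one such surgery and 2 bleeds elsewhere in follow-up.

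- 365.25 days followed, 1 bleed in the post-surgery interval: literal 3 / 358.25 × 365.25 = 3.06; intended 2 / 351.25 × 365.25 = 2.08.
- 365.25 days followed, no bleed in that interval: literal 2 / 358.25 × 365.25 = 2.04; intended 2.08.
- 730.5 days followed, 1 bleed in that interval: literal 3 / 723.5 × 365.25 = 1.51; intended 2 / 716.5 × 365.25 = 1.02.

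For consumption, D0 and any further dose before D1 are counted under the literal bullet and excluded under the intended reading.

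**Step 6, where the fault does not arise.** The same rules give a proper period in each of these variants:

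- all four dates are missing, so the fallback bullet applies;
- discharge is on a later day;
- a later post-operative visit is recorded;
- the comparison uses a recorded discharge time;
- the covering dose was given the day before;
- the dose has been relabelled as surgical.

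**Step 7, consistency within the section.** The literal result conflicts with three other places in SAP 5.3.3: the opening sentence, which requires a dose later than the last day; the fallback, which requires a dose later than the end of surgery; and the division of the total period, whose intraoperative part runs from the pre-surgery dose to the end of surgery. A period ending at 07:59 cannot contain that part. A surgery with a recorded discharge date is thus handled worse than one with no dates at all.

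**The case against.** The strongest reply is that the case is rare and the intent is plain. Several conditions must hold together, and each can fail.

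- Major surgery requires a visit 1 to 2 weeks afterwards (SAP 3.1), so its last date lies well past the day of surgery.
- Pre-surgery doses are expected to carry a surgical label, and the change codes in SAP 9 allow a routine label to be changed to a surgical one without subject confirmation.
- Minor procedures such as dental extractions may have no hospital discharge date, and the fallback then works.
- SAP 7.6 lists discharge times, and the third end bullet imputes 23:59 only where a date has no time. That suggests recorded times may be used, and with a 15:00 discharge time the fault disappears.

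All of this stands as a limit on scope. It does not remove the defect. The second start bullet exists because some pre-surgery doses keep a routine label. The main end bullet speaks of dates, while the bullet after it speaks of date and time. A programmer following the text would compare dates.

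A reader might infer two further consequences. One is that the wrong interval leaves the efficacy period, with the clean interval dropped in exchange for the surgical one. The documents do not support this: SAP 5.3.2 removes the pre-surgery interval deliberately under every reading, and the fix below would still remove it. The other is that minor-surgery tables would show no injections. That is not shown either, because SAP 7.6 counts the pre-surgery dose as given during surgery and defines the day of surgery by calendar day, independently of the period's end.

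**Conclusion.** The point holds in a narrow form. As worded, the main end bullet gives a surgical/rehabilitation period of -1 minute when four conditions meet: a recorded discharge date equal to the surgery date, no later visit or rehabilitation date, a same-day pre-surgery dose still labelled routine prophylaxis, and comparison by date. In practice this means minor surgery. It does not extend to day-case surgery in general, as a reader might assume.

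Per affected surgery, one post-surgery dosing interval of k days, with any bleeds and doses in it, is wrongly kept. Without a bleed in that interval the illustrated one-year ABR moves only from 2.08 to 2.04; with one it moves to 3.06. These figures rest on the assumed bleeds and follow-up, and they shrink with longer participation, which can run to 4 years. The documents do not say how many surgeries are affected, so the total effect cannot be computed and is probably small. All analyses are descriptive, and the primary endpoint, inhibitor development, is untouched. Correction is still worthwhile: the rule is wrong as stated, it conflicts with its own section, and it feeds two secondary endpoints.

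**What to change.** Reword the main end bullet for prophylactic regimens in SAP 5.3.3. The period should end 1 minute before the first prophylactic dose that meets both conditions:

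- it is after the end date and time of surgery (23:59 on the surgery date if the time is missing or 00:00);
- it is on or after the last of the four dates (discharge, post-operative visit 1, post-operative visit 2, end of rehabilitation).

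Word the opening sentence of the section to match, so that the two no longer differ on a dose given on the last day itself. Add a program check that every surgical/rehabilitation period ends later than it starts, and list any that fail.

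The cost is one sentence of SAP text, one program condition and one check. No new data are needed. The condition brings the main bullet into line with the SAP's own fallback for missing dates, and periods whose end dose already follows the surgery do not change.

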All major surgeries must take place in a center that can provide study treatment, trained study personnel, post-operative assessments and hematological consultation by the Investigator or Sub-investigator. If surgery does not take place in such a setting, the subject will be withdrawn from the study. Specific provisions apply when a subject requires major surgery.

Surgeries, elective or emergent, will be classified as major and minor as follows:

- Major surgery is defined as any surgical procedure (elective or emergent) that usually, but not always, involves general anesthesia and/or respiratory assistance, in which a major body cavity is penetrated and exposed, or a substantial impairment of physical or physiological functions is produced (e.g., laparotomy, thoracotomy, craniotomy, joint replacement, or limb amputation).
- Minor surgery is defined as any surgical procedure (elective or emergent) that does not involve general anesthesia and/or respiratory assistance (e.g., minor dental extractions, incision, and drainage of abscess, joint or other injections, or simple excisions).

All major surgeries will be reported as serious adverse events (SAEs).

Rehabilitation period

CONFIDENTIAL

The information contained herein may not be used, disclosed, or published without the written consent of Biogen Idec MA Inc.

If surgery-related dosing is to be continued during post-operative rehabilitation, the dose of rFIXFc will be adjusted to achieve a trough at a sufficient level to maintain hemostasis, including during physical therapy. These doses will be captured in the subject's electronic patient diary (eDiary).

Subjects will return to a regular rFIXFc regimen once all dosing for the post-operative period has been completed. For subjects undergoing major surgery, a visit is required 1-2 weeks after surgery (Visit 3). Visit 4 (Last Post-Operative Visit) occurs when the subject returns to a regular rFIXFc regimen as determined by the Investigator, and is required only if the subject did not return to a regular rFIXFc regimen at Visit 3. For minor surgery, Visits 3 and 4 are not performed.

Study Location:	Global
Number of Planned Subjects:	Approximately 120 subjects are planned to be treated in the study.
Study Population:	This study will be conducted in previously treated adult and pediatric subjects with hemophilia B who have participated in a previous rFIXFc clinical study. Detailed criteria are described in the body of the protocol.

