5.3.3. Surgery and Rehabilitation

If a subject requires emergent or elective surgery while participating in this study, he may be treated with the dose and regimen of rFIXFc deemed appropriate for the type of surgery. All major surgeries will be reported as SAEs.

All major surgical procedures must take place in a center that can provide study treatment, trained study personnel, post-operative assessments, and hematological consultation by the Investigator or Sub-Investigator. If the surgery does not occur in such a setting, the subject will be withdrawn from the study. See Section 10.1.3 for provisions for when a subject requires major surgery.

If surgery-related dosing is continued during post-operative rehabilitation and/or physical therapy, the dose of rFIXFc will be adjusted to achieve a trough at a sufficient level to maintain hemostasis.

Subjects will return to a regular rFIXFc regimen once all dosing for the post-operative rehabilitation period has been completed. For subjects undergoing major surgery, a visit is required 1-2 weeks after surgery (Visit 3). Visit 4 (Last Post-Operative Visit) occurs when the

CONFIDENTIAL

The information contained herein may not be used, disclosed, or published without the written consent of
Biogen Idec MA Inc.

subject returns to a regular rFIXFc regimen, as determined by the Investigator, and is required only if the subject did not return to a regular rFIXFc regimen at Visit 3. For minor surgery, Visits 3 and 4 are not performed.

The surgical period will begin with the subject's first dose of rFIXFc given for the surgery (i.e., the pre-surgery dose). This is the pre-operative period of the surgery. The intra-operative period is defined as the time the surgery begins, to the time the surgery completes. The post-operative care period is defined as the time period following the completion of the surgery through the last dose of rFIXFc given for the surgery, as judged by the Investigator/Surgeon, including doses given to prevent bleeding during the post-operative rehabilitation period.

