6.5.4. Consumption

The total annualized rFIXFc consumption (IU/kg) will be calculated for each subject using the following formula:

$$\text{Annualized consumption} = \frac{\text{Total IU/kg of study drug received during the efficacy period}}{\text{Total number of days during the efficacy period}} \times 365.25$$

The total amount of rFIXFc received will be the sum of the nominal IU/kg administered for each injection based on the units of rFIXFc as recorded from the subject’s diary and eCRF and his most recent weight.

Total annualized rFIXFc consumption will be determined for each treatment regimen during the efficacy period (i.e., excluding surgery/rehabilitation periods [major and minor surgeries]).

For personalized prophylaxis regimen, additional injections administered will be included in the consumption calculations.

Consumption is a secondary endpoint in this study. A description of how consumption will be summarized is provided in Section 7.3.3.

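### When the episodic regimen follows surgery, the SAP's rule for ending the surgical period ignores the last surgical dose, so later surgical doses can count as on-demand consumption, mainly after minor surgery or with missing or early dates

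*SAP*

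**What the plan says.** SAP 5.3.3 sets the end of the surgical/rehabilitation period according to the regimen that follows surgery. If that regimen is episodic, the end is 23:59 of the "last date among the dates for discharge from the hospital, post-operative visit 1, post-operative visit 2, and the end of rehabilitation". The fallback reads: "If all of the dates mentioned above are missing, then select the date of the end of surgery and impute 23:59 for the time". Where surgery has no recorded end date either, its start date is used. The section adds: "The surgical/rehabilitation period will be determined in the same manner for both major and minor surgeries".

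SAP 5.3.3 also divides the total period into parts, and runs the post-operative care part "to the last dose of rFIXFc given for the surgery, including doses given to prevent bleeding during the post-operative period". Protocol 5.3.3 likewise runs post-operative care "through the last dose of rFIXFc given for the surgery, as judged by the Investigator/Surgeon". On visits, the Protocol Synopsis states: "For minor surgery, Visits 3 and 4 are not performed".

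The end date feeds two secondary endpoints. Under SAP 5.3.2, episodic efficacy time starts or restarts "at 00:01 on the day following the end of the surgical/rehabilitation period". SAP 6.5.4 takes as the consumption numerator "Total IU/kg of study drug received during the efficacy period", summed over injections with no filter on the reason for injection. SAP 7.1.1 divides bleeds in the efficacy period by days in that period to obtain the ABR.

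**The concern.** SAP 6.5.4 and 7.1 intend to keep surgical periods, major and minor, out of consumption and bleeding summaries. The only tool for doing so is the pair of dates that bound the period. For surgery followed by the episodic regimen, the closing date does not depend on when surgical dosing stopped. If dosing for the surgery continues past it, those doses become on-demand consumption and those days become on-demand time at risk.

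The section also cannot then be programmed as written. Post-operative care would outlast the period said to contain it, and the rehabilitation part, which begins the day after post-operative care, would begin after its own end.

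At stake are the episodic columns for annualized consumption and ABR. The prophylaxis end rule is normally tied to the next prophylactic dose, so the two kinds of regimen are tabulated under different closing rules.

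**Working it through.** The plan states no figure to reproduce, so the check traces the rule and then sizes a leak on assumed inputs.

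**Step 1: is there a dose term anywhere?** The episodic end rule has four dates and a surgery-day fallback, none of them a dose. The general description of the broadest span in SAP 5.3.3 does not help: for episodic subjects it refers to the last day of the period itself, which is circular. The same section reclassifies surgical-labelled doses that match no surgery, but it gives doses that do match no role in the episodic end. Nothing in SAP 6.5.4 or 7.1.1 removes them later.

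**Step 2: can the gap be reached?**
- Major surgery: Protocol 5.3.3 and 10.1.3 require Visit 3 at 1–2 weeks, and Visit 4 if the subject is not yet back on a regular regimen. That return follows completion of post-operative dosing, so the latest date should normally cover the surgical doses.
- Minor surgery: taking the SAP's post-operative visits 1 and 2 to be Visits 3 and 4, only a discharge or end-of-rehabilitation date can extend the period. With neither, the period closes on the surgery day.

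An example is a minor procedure on day 0 with no discharge or rehabilitation date and a surgical dose on day 2. The period ends at 23:59 on day 0 and efficacy time restarts at 00:01 on day 1, so the day 2 dose counts as on-demand consumption. Post-operative care ends on day 2, and the rehabilitation part would start on day 3 and end on day 0.

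**Step 3: effect on consumption.** Let C be the subject's true on-demand consumption per year, T the efficacy days including d leaked days, and k leaked doses of D IU/kg.

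Observed = [C × (T − d)/365.25 + k × D] / T × 365.25

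C, k, D, d and T are assumptions; the documents give none of them. With C = 1000 IU/kg/year:

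| T | Leak | Observed | Change |
|---|---|---|---|
| 365.25 days | 1 × 50 over 2 days | 994.5 + 50 = 1044.5 | +4.5% |
| 365.25 days | 3 × 50 over 7 days | 980.8 + 150 = 1130.8 | +13.1% |
| 1461 days | 1 × 50 over 2 days | 1011.1 | +1.1% |
| 1461 days | 3 × 50 over 7 days | 1032.7 | +3.3% |

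The leaked days also enter the denominator, so one 50 IU/kg dose over one year adds 44.5, not 50.

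For C from 500 to 2000 IU/kg/year, T from 0.5 to 4 years, and leaks from 1 × 50 over 2 days to 5 × 100 over 14 days, the overstatement runs from about 0.5% (C = 2000, 4 years, smallest leak: 2009.8) to about 192% (C = 500, half a year, largest leak: 1461.7).

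**Step 4: effect on ABR.** With no bleed in the leaked days, ABR is multiplied by (T − d)/T. Over one year that is −2/365.25 = −0.55% or −7/365.25 = −1.92%. One treated bleed in those days adds 365.25/T to the rate, which is 1.0 per year over one year or 0.25 over four. Protocol 10.1.3 requires undesired or unexpected bleeding after surgery to be recorded, so the direction is not fixed.

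**The case against.** The strongest reply is that the rule works where it matters most. In major surgery the last post-operative visit is tied to return to the regular regimen and so stands in for the end of surgical dosing. That stands, provided the visits take place as planned and the dates are recorded.

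For minor surgery, the planned outputs include a hospitalization listing, so some discharge dates should exist. The minor-surgery dosing listing covers only dosing during surgery and on that day, which suggests little later dosing was expected. That lowers the likely frequency but does not exclude the case, and that listing would not show later doses if they occurred.

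A reader might infer more than the documents support:
- That on-demand subjects who have surgery leak doses in general. A leak needs a surgical dose after the latest of all four dates, or after the surgery day if all are missing. The rule also depends on the regimen after surgery, not before it.
- That on-demand ABR is biased downward. Step 4 shows it can rise.
- That contrasts between prophylaxis and on-demand are biased. Protocol 16 plans no formal comparison and SAP 7.1.2 no tests on efficacy endpoints; consumption is only summarized by regimen.
- That the prophylaxis rule has the same fault. When a later prophylactic dose exists, the period runs to just before it, and no defect is shown there.

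**Conclusion.** The point holds in a limited form. For surgery followed by the episodic regimen, the SAP 5.3.3 end rule has no last-surgical-dose term, conflicts with the sub-periods in its own section and with Protocol 5.3.3, and nothing downstream corrects it. Exposure is mainly minor surgery without post-operative visits and cases with missing or early dates.

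For an affected subject, annualized consumption is overstated in every case calculated, by about 4.5% to 13% in the one-year illustrations. The effect on ABR is small in those illustrations if no bleed falls in the leaked days, and its sign is open. All sizes rest on assumed doses, days, follow-up and underlying consumption. The documents do not show how many subjects are affected, so no effect on a regimen-level summary can be given. This is a correction worth making to a secondary endpoint; it does not touch the primary inhibitor endpoint.

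**What to change.** In SAP 5.3.3, when the episodic regimen follows, end the period at 23:59 on the later of (a) the date given by the present rule, including the surgery-day fallback, and (b) the date of the last rFIXFc dose recorded for that surgery. State how a surgical-labelled dose is linked to a surgery. SAP 5.3.3 does this for pre-surgical doses but not for later ones. The link should not itself depend on the surgical period, because the change codes in SAP 9 refer to that period when routine doses are relabelled as surgical.

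An alternative is to exclude surgical-labelled doses linked to a surgery from episodic consumption. That corrects the numerator but leaves the covered days in the consumption and ABR denominators and does not reconcile the sub-periods, so the first option is better. No change to the prophylaxis rule is shown to be needed.

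The cost is a few sentences and a small program change. Reasons for injection are already recorded (SAP 6.5) and surgical labels already set the start of the period. This concerns the analysis window only and alters no treatment rule.
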